10. APPENDICES

10.1 DIAGNOSIS OF ANAPHYLAXIS

Clinical Criteria for diagnosing anaphylaxis [\[R11-4890\]](#)

Anaphylaxis is highly likely when any one of the following 3 criteria are fulfilled
1. Acute onset of an illness (minutes to several hours) with involvement of the skin, mucosal tissue, or both (eg, generalized hives, pruritus or flushing, swollen lips-tongue-uvula)
AND AT LEAST ONE OF THE FOLLOWING
a. Respiratory compromise (eg, dyspnea, wheeze-bronchospasm, stridor, reduced PEF, hypoxemia)
b. Reduced BP or associated symptoms of end-organ dysfunction (eg, hypotonia [collapse], syncope, incontinence)
2. Two or more of the following that occur rapidly after exposure to a likely allergen for that patient (minutes to several hours):
a. Involvement of the skin-mucosal tissue (eg, generalized hives, itch-flush, swollen lips-tongue- uvula)
b. Respiratory compromise (eg, dyspnea, wheeze-bronchospasm, stridor, reduced PEF, hypoxemia)
c. Reduced BP or associated symptoms (eg, hypotonia [collapse], syncope, incontinence)
d. Persistent gastrointestinal symptoms (eg, crampy abdominal pain, vomiting)
3. Reduced BP after exposure to known allergen for that patient (minutes to several hours):
a. Infants and children: low systolic BP (age specific) or greater than 30% decrease in systolic BP*
b. Adults: systolic BP of less than 90 mm Hg or greater than 30% decrease from that person's baseline

PEF, Peak expiratory flow; BP, blood pressure.

*Low systolic blood pressure for children is defined as less than 70 mm Hg from 1 month to 1 year, less than (70 mm Hg +[2 x age]) from 1 to 10 years, and less than 90 mm Hg from 11 to 17 years.

11. DESCRIPTION OF GLOBAL AMENDMENT(S)

11.1 GLOBAL AMENDMENT 1

Date of amendment	04 July 2022
EudraCT number EU number	2020-005587-55
BI Trial number	1368-0067
BI Investigational Product(s)	BI 655130
Title of protocol	An open-label, long-term extension trial of spesolimab treatment in adult patients with Hidradenitis Suppurativa (HS)
Global amendment due to urgent safety reasons	No
Global amendment	X

Section to be changed	CLINICAL TRIAL PROTOCOL SYNOPSIS, Trial Endpoints, 2.1.3 Secondary endpoints(s)
Description of change	
Change the wording in two endpoints FROM: Number of patients having at least one flare (defined as at least [REDACTED] in AN count with a minimum increase of 2 relative to baseline) up to Week [REDACTED] Number of patients having at least [REDACTED] from baseline in Numerical Rating Scale (NRS30) in Patient's Global Assessment of HS Pain up to Week [REDACTED]
 
TO: Occurrence of at least one flare (defined as at least [REDACTED] in AN count with a minimum [REDACTED] of [REDACTED] relative to baseline) up to Week [REDACTED]. Achievement of at least [REDACTED] from baseline in Numerical Rating Scale (NRS30) in Patient's Global Assessment of HS Pain up to Week [REDACTED]

Rationale for change	To better clarify and to make these two secondary endpoints more informative.

Section to be changed	Flow Chart - Up to W [REDACTED]
Description of change	Add footnote about dose modification at Week 12
Rationale for change	To align with Table 3.1: 1 and instructions in section 3.1

Section to be changed	Flow Charts, Footnotes #8 and #17, Section 5.1.1
Description of change	Added information that the HiSCR value is

		calculated automatically.
Rationale for change		To clarify that the HiSCR value is not required to be completed by the investigator.

Section to be changed		Flow Chart - W█████ to End of study, Section 3.3.4 Withdrawal of patients from treatment, 6.2.3 Follow-up period and trial completion
Description of change		Align wording FUP1 and EoS visit timelines with Flow Chart. FUP 1 is two weeks after last dose and EOS is █████ weeks after last dose.
Rationale for change		To have consistent wording

Section to be changed		Flow Chart – W█████ to End of Study
Description of change		Add footnote ***. Clarification on re-assessment of Non-responders on ████████ at Week █████
Rationale for change		To align with the information in Table 3.1: 1.

Section to be changed		Table 1.4.2:1 Risks
Description of change		The risk “Peripheral Neuropathy” was added to Table 1.4.2:1 including a summary of data and mitigation strategy.
Rationale for change		Added to inform about the newly added potential risk “peripheral neuropathy” deriving from the three cases reported as Guillain-Barré syndrome by the investigator in Spesolimab trials (details in the CTP). The cases were considered as peripheral neuropathy by the external neurologist expert panel’s assessment.

Section to be changed		3.3.4.1 Discontinuation of trial treatment
Description of change		Include the discontinuation of Non-responders on ████████ at Week █████
Rationale for change		To be consistent with Table 3.1: 1

Section to be changed		3.3.4.1 Discontinuation of trial treatment
Description of change		The patient needs to take concomitant medication such as immunosuppressive biologics, systemic corticosteroids, other immunomodulators, opioid analgesics for HS, live vaccines, or other concomitant medication that interferes with the Investigational Medicinal Products (IMP) or other trial treatment.
Rationale for change		To be consistent with Table 4.2.2.1: 1 – Restricted Medication.

Section to be changed		3.3.4.1 Discontinuation of trial treatment
Description of change		Added language in bold i.e. The patient can no

		longer receive trial treatment for medical reasons such as surgery, serious or severe Drug Induced Liver Injury attributable to the trial drug, other adverse events, other diseases, or pregnancy. Also refer to Section 5.2.6.1.4 .
Rationale for change		To use standard language.

Section to be changed		4.1.4, 7 th paragraph
Description of change		Add the name of the exact document, i.e., Instructions for Pharmacist, which is found in the ISF.
Rationale for change		To clarify the name of the document in the ISF.

Section to be changed		4.2.1.4 Peripheral Neuropathy
Description of change		Following information was added: “Peripheral Neuropathy” If peripheral neuropathy is suspected, treatment with Spesolimab should be temporarily discontinued until a full neurological investigation has been conducted. After completion of the neurological investigation, treatment can be restarted based on medical judgement of the investigator.
Rationale for change		Added as mitigation strategy to account for the three cases reported as Guillain-Barré syndrome in spesolimab trials. The cases were considered as peripheral expert panel’s assessment (details in the CTP).

Section to be changed		Table 4.2.2.1: 1 – Restricted Medications
Description of change		Move footnote #6 to “Restricted for HS”
Rationale for change		To clarify that topical corticosteroids are allowed prior to Week █ for non-HS areas only.

Section to be changed		4.2.1.1, 3 rd paragraph
Description of change		Add the name of the exact document, i.e., Instructions for Pharmacist, which is found in the ISF.
Rationale for change		To clarify the name of the document in the ISF.

Section to be changed		4.2.1.1, 4 th paragraph
Description of change		Add the name of the exact document, i.e., Use of Spesolimab Pre-filled Syringes, which is found in the ISF.
Rationale for change		To clarify the name of the document in the ISF.

Section to be changed		4.2.2.1
------------------------------	--	---------

Description of change	(W0 - W and W through to EoT).
Rationale for change	Change W to W to match the headings in the Restricted Medications Table 4.2.2.1: 1

Section to be changed	4.2.2.2
Description of change	If a patient receives rescue treatment, the decision to maintain the patient on trial treatment is based on the investigator's clinical judgement.
Rationale for change	To remove the need for the investigator to discuss their decision with the sponsor.

Section to be changed	4.2.2.4
Description of change	Opiate analgesics (except synthetic opioids such as tramadol) are restricted for HS. It can be allowed for non-HS indications as per investigator discretion
Rationale for change	This is a 2-year OLE trial with a primary endpoint of TEAE. Tramadol is added to allow for pain relief for HS or non-HS indications to help patients over this 2-year period.

Section to be changed	4.2.2.7 Contraception Requirements
Description of change	Remove the following sentence: A double barrier method of contraception is not required.
Rationale for change	Sentence is redundant and confusing. The acceptable methods of birth control are defined in this section.

Section to be changed	5.2.3 Safety laboratory parameters
Description of change	If blood sampling for central lab is not possible because central laboratory supplies are not available on time, safety lab analyses can be performed at a local laboratory. The results of the local lab tests must be reported to the investigator who ensures medical review and proper documentation in the eCRF.
Rationale for change	To prevent that an important safety laboratory analysis is not done and allow local safety analysis in emergency

2. LIST OF ABBREVIATIONS

See Medicine Glossary:

<http://glossary>

Term	Definition / description
ADA	Anti-drug antibodies
ADS	Analysis dataset
AdT	total abscess, inflammatory nodule and draining tunnel
AE	Adverse event
AESI	Adverse event of special interest
ALQ	Above the upper limit of quantification
ALT	Alanine aminotransferase
AN	Abscess and inflammatory nodule
ANdT	Abscess, inflammatory nodule and draining fistula/tunnel
AP	Alkaline phosphatase
AST	Aspartate aminotransferase
ATC3	Anatomical-Therapeutic-Chemical classification level 3
AUC _{0-∞}	Area under the concentration-time curve of the analyte in plasma over the time interval from 0 extrapolated to infinity
BI	Boehringer Ingelheim
BLQ	Below the lower limit of quantification
BMI	Body mass index
BSA	Body surface area
CARE	Clinical data analysis and reporting environment
CGI	Clinical Global Impression
C _{max}	Maximum measured concentration of the analyte in plasma
CRF	Case report form
CRP	C-reactive protein
CTA	Clinical Trial Application
CTP	Clinical trial protocol
CTR	Clinical trial report
CV	Arithmetic coefficient of variation
DBLM	Database lock meeting

Term	Definition / description
DMC	Data monitoring committee
DNA	Deoxyribonucleic acid
EC	Estimand concept
ECG	Electrocardiogram
eCRF	Electronic case report form
EMA	European Medicines Agency
ES	Enrolled set
EudraCT	European union drug regulating authorities clinical trials
FACIT	Functional Assessment of Chronic Illness Therapy
FUP	Follow-up
gCV	Geometric coefficient of variation
GCP	Good Clinical Practice
gMean	Geometric mean
GPP	Generalized pustular psoriasis
HASI	HS Area and Severity Index
HS	Hidradenitis suppurativa
HS-PGA	HS Physician Global Assessment
HiSCR	Hidradenitis suppurativa clinical response
m-HiSCR	Modified - Hidradenitis suppurativa clinical response
HS-CRP	High-Sensitivity C-Reactive Protein
IHS4	International Hidradenitis Suppurativa Severity Score System
IHS4-55	At least a 55% reduction from baseline in IHS4
IL-36	Interleukin 36
IL-36R	Interleukin 36 Receptor
NRS	numerical rating scale
ICH	International Council for Harmonisation of Technical Requirements for Pharmaceuticals for Human Use
HiS-QoL	Hidradenitis suppurativa quality of life
iPD	Important protocol deviation
ICEs	Intercurrent events
i.v.	intravenous
MAA/BLA	Market Authorization Application/Biologics Licence Application

Term	Definition / description
MedDRA	Medical Dictionary for Regulatory Activities
DLQI	Dermatology Life Quality Index
Nab	Neutralising antibody
NRI	No response imputation
OC	Observed cases
OR	Original results
OLE	Open Label Extension
PD	Pharmacodynamic(s), protocol deviation
PE	Primary endpoint
PK	Pharmacokinetic(s)
PKS	Pharmacokinetic parameter set
PPS	Per protocol set
PT	Preferred term
Q1	1 st quartile
Q3	3 rd quartile
RAGe	Report appendix generator
REP	Residual effect period
RNA	Ribonucleic acid
RPM	Report planning meeting
SAE	Serious adverse event
SD	Standard deviation
SDL	Subject data listing
SI	Système international d'unités
SOC	System organ class
TS	Treated set
TSAP	Trial statistical analysis plan
UDAEC	User-defined Adverse Event Category
ULN	Upper limit of normal range
VAS	Visual analogue scale
MCMC	Markov Chain Monte Carlo

3. INTRODUCTION

As per ICH E9, the purpose of this document is to provide a more technical and detailed elaboration of the principal features of the analysis described in the protocol, and to include detailed procedures for executing the statistical analysis of the primary and secondary variables and other data.

This TSAP assumes familiarity with the Clinical Trial Protocol (CTP), including Protocol Amendments. In particular, the TSAP is based on the planned analysis specification as written in CTP Section 7 “Statistical Methods and Determination of Sample Size”. Therefore, TSAP readers may consult the CTP for more background information on the study, e.g., on study objectives, study design and population, treatments, definition of measurements and variables, planning of sample size, randomization.”

The statistical analyses will be performed within the validated working environment CARE, including SASTM (current Version 9.4, by [REDACTED]), and a number of SASTM-based tools (e.g., macros for the analyses of AE data or laboratory data; Report Appendix Generator system (RAGe) for compilation/formatting of the CTR appendices).

Analyses of the biomarker and gene expression data are described in a separate biomarker TSAP, unless otherwise specified in this document.

Since the primary aim of this study is to collect long-term safety and efficacy data on the use of spesolimab (BI 655130) in adult patients with Hidradentis suppurativa (HS), 1 interim analysis when all the rolled over patients reach Week 12 in this trial will be done over the 2-year conduct phase of this trial in order to support, for example, regulatory interactions, Clinical Trial Applications (CTA), and Market Authorization Application/Biologics Licence Application (MAA/BLA) submissions, but also to provide important safety and efficacy information to the sponsor to guide further development of the compound, and to the investigators via IB updates and publications. Any data cut-off to be used for the reporting of trial data at interim will be presented in either a separate data cleaning plan, or in an appendix to this TSAP. If considered appropriate, an access plan may be developed at the time of the interim which describes those personnel who will be allowed access to the results of the interim data analysis.

4. CHANGES IN THE PLANNED ANALYSIS OF THE STUDY

All analyses stated in the CTP (latest version) will be performed as planned with the following adaptations.

Considering the categorical nature of PGI-S and PGI-C, the frequency over time will be presented for these further endpoints instead of absolute change from baseline as planned in CTP.

The below further efficacy endpoints, which were not specified in the CTP, have been added:

- Percent change from baseline (%) in total abscess and draining fistula (AdT) count over time.
- Percent change from baseline (%) in total abscess, inflammatory nodule and draining fistula/tunnel (ANdT) count over time.
- Proportion of patients with achievement of m-HiSCR response over time.
- Proportion of patients with achievement of IHS4-55 response over time.
- Percent change from baseline (%) in total inflammatory nodule count up over time.
- Percent change from baseline (%) in total abscess count up to over time.
- Achievement of complete elimination of draining fistulas over time.
- Achievement of complete elimination of abscess over time.
- Proportion of patients with achievement of HiSCR over time.
- At least 30% reduction from baseline in Numerical Rating Scale (NRS30) in Patient's Global Assessment of HS Pain over time.

5. ENDPOINTS(S)

For estimand and handling of missing data and the occurrence of inter-current events, unless otherwise specified, see [Section 6.3](#), [Section 6.4](#) and [Section 6.6](#). For the specification of baseline definition, unless otherwise specified, see [Section 6.7](#).

For the summary of all efficacy data, only those observations which were collected during the on-treatment period will be used.

Baseline for safety data, unless otherwise specified, is the last value prior to initiation of treatment in current 1368-0067 study.

Regarding the analyses of the change from baseline by visit or compared to baseline by visit for efficacy endpoints, unless otherwise specified, we will use last measurement collected prior to initiation of spesolimab as baseline. i.e.,

- For prior spesolimab arm in 1368-0052, the baseline in parent trial is used, which refers to the last measurement collected prior to initiation of treatment in 1368-0052.
- For prior placebo arm in 1368-0052, the baseline in current trial is used, which refers to the last measurement collected prior to initiation of treatment in 1368-0067.

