3. DESCRIPTION OF DESIGN AND TRIAL POPULATION

3.1 OVERALL TRIAL DESIGN

This open label, single-arm, multi-regimen, 2-year extension study investigates the long-term safety and efficacy of spesolimab in patients with HS who have completed their treatment in the 1368-0052 PoCC trial. BI trial 1368-0052 is the first trial from which patients will rollover into this extension trial. Patients rolling over into this trial must have completed the treatment period as required in the 1368-0052 PoCC trial. Ideally, the end of treatment (EoT) visit of the preceding trial is the baseline visit (V1) of this extension trial.

This extension trial consists of a [REDACTED] weeks treatment period followed by a [REDACTED] week safety follow-up period.

Approximately [REDACTED] patients from the 1368-0052 PoCC trial are planned to be rolled over into this open-label extension study.

Patients from the placebo arm of the 1368-0052 PoCC trial will be given an initial [REDACTED] dose of spesolimab plus [REDACTED] placebo, followed by [REDACTED] spesolimab [REDACTED] every [REDACTED] weeks [REDACTED]). Patients from the active arm of the 1368-0052 PoCC trial will be given an initial [REDACTED] placebo plus [REDACTED] spesolimab [REDACTED], followed by [REDACTED] spesolimab [REDACTED] every [REDACTED]. Administration of trial medication at Visit 1 is blinded. See [Section 3.1.1](#) for more details.

[figure not shown]
At Week [REDACTED] of this extension trial, all patients will be assessed for the change of HS-PGA grade. The change in HS-PGA grade will be compared with the assessment at baseline of this extension trial / Week [REDACTED] of the 1368-0052 PoCC trial. Based on the individual responder status decisions on further dosing will be taken as depicted in [Table 3.1: 1](#).

Table 3.1: 1 Week 12 Dose Modification Management

Baseline	Assessment at Week 12	Management
Status from Week 12 of 1368-0052 PoCC trial	HS-PGA grade change from baseline HS-PGA grade of this trial	
Responder (Achieved HiSCR 50)	No change or improvement in grade (i.e., reduction by at least 1 grade)	Continue the same dose
	Worsening in grade (i.e., increase by at least 1 grade)	Option to increase the dose to [REDACTED]
Partial Responder (Achieved HiSCR 25 but did not achieve HiSCR 50)	Improvement in grade	Continue the same dose
	No change or worsening in grade	Increase the dose to [REDACTED]
Non-responder (Did not achieve HiSCR 25)	Improvement in grade	Continue the same dose

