4.1.2 Selection of doses in the trial and dose modifications

In the 1368-0052 PoCC trial, a fixed rather than weight-based dose regimen was selected. Early trials of therapeutic monoclonal antibodies often investigate bodyweight-based regimens to reduce the inter-subject variability in drug exposure. However, there is generally only a modest contribution of body weight to the overall PK and PD variability of monoclonal antibodies. Furthermore, monoclonal antibodies are highly target specific and offer a relatively large therapeutic window compared to new chemical entities. Therefore, most monoclonal antibodies are approved at fixed doses in antibody/target excess in order to cover target turnover and maximize efficacy [R10-6267; R13-4749; R13-4753; R13-4750; R13-4754].

In this extension trial, patients from the active arm in the parent trial will be given [REDACTED] every [REDACTED], which is half the dose of the 1368-0052 PoCC trial. This is to evaluate whether these patients would be able to sustain efficacy at a lower dose. Patients who were in the placebo arm will be given a [REDACTED] dose of spesolimab, followed by [REDACTED] every [REDACTED]. The rationale is to give an opportunity to the patients from the placebo arm to be given active treatment and also to understand induction response after a placebo period. Additionally, this dose was also selected to evaluate efficacy of [REDACTED] dose. All the patients will be reassessed at Week [REDACTED] to evaluate the response and will have the option of either continuing the same dose or increasing the dose.

Data from the 1368-0052 PoCC trial will not be available prior to the 1st patient rolling over into this extension trial. When new data from the PoCC trial becomes available, the impact for this extension trial will be evaluated and if needed the dose would then be adjusted by amending this protocol.

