Laboratory data will be analysed both quantitatively as well as qualitatively. The latter will be done via comparison of laboratory data to their reference ranges. Values outside the reference range as well as values defined as clinically relevant will be highlighted in the listings.

Vital signs, physical examinations, or other safety-relevant data observed at baseline, during the course of the trial and at the end-of-trial evaluation will be assessed with regard to possible changes compared to findings before start of treatment.

Immunogenicity data will be analysed in a descriptive way.

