7.8.2 Laboratory data

The analyses of laboratory data will be descriptive in nature and will be based on BI standards [\(12\)](#). Note that data from the central Laboratory will be used for all displays described below, unless otherwise specified.

For continuous safety laboratory parameters, normalized values will be derived. Normalisation means transformation to a standard unit and to a standard reference range. The process of normalisation, handling of repeat values at the same visit for by-visit displays, as well as standard analyses for safety laboratory data are described in the BI guidance for the Display and Analysis of Laboratory Data [\(12\)](#). All analyses considering multiple times of the ULN (as described below) will be based on standardized and not normalized values. For continuous safety laboratory parameters, differences to baseline will be calculated. For all outputs, the last assessment before the first treatment at Day 1 is chosen as the baseline value.

Only patients with at least one available post-baseline value will be included in the analysis of an individual laboratory parameter. All individual laboratory data will be listed. Values outside the reference range will be flagged.

For derivation of the last value, the minimum value, and the maximum value, all values during the entire treatment period will be considered under OR. These will be derived for analysis of laboratory, vital signs and local tolerability data. For identification of potentially clinically significant abnormal laboratory values, all values during entire treatment period will also be considered under OR.

Descriptive statistics of laboratory values over time and for the difference from baseline on-treatment (see [Section 6.7](#)) will be based upon normalized values and provided by visit (including follow up) under OC-IR, including summaries of the last value on-treatment, the minimum value on-treatment, and the maximum value on-treatment. Graphical displays via box plots will be produced for the change from baseline, over time, for each continuous laboratory endpoint.

Laboratory values will be compared to their reference ranges; shift tables will be provided for the number of patients with a specific RCTC grade at baseline versus the grade at the last measurement on treatment, as well as the worst grade on treatment. These analyses will be based on standardized laboratory values.

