Potentially clinically significant abnormalities will be identified based on BI standard rules which are based on converted lab values, i.e. using SI units. These rules will be listed in the SDL appendix of the CTR. Frequency tables will summarize the number of patients with potentially clinically significant abnormalities. Patients having an abnormal lab value at baseline will be presented separately. A separate listing will present potentially clinically significant abnormal lab values; for each functional lab group all patient's lab values will be listed, if there exists at least 1 lab value with clinically significant abnormality within the group.

The frequency of patients with AST or ALT elevations $\geq 3xULN$, $\geq 5xULN$, $\geq 10xULN$, and $\geq 20xULN$ will be displayed based on standardized laboratory values. To support analyses of liver related adverse drug effects, the frequency of patients with AST and/or ALT $\geq 3xULN$ combined with a total bilirubin $\geq 2xULN$ in a 30 day period after AST/ALT elevation will be displayed, stratified by alkaline phosphatase $< 2xULN$ and $\geq 2xULN$ (a patient can potentially be in both alkaline phosphatase strata in case of multiple AST/ALT and bilirubin elevations). The start of the 30 day time span is triggered by each liver enzyme elevation above the defined thresholds. This analysis will be based on standardized laboratory values.

A graphical analysis of the ALT, AST and total bilirubin during the on-treatment period will also be performed; the so called eDISH plot. In the graph, for each subject, the peak total bilirubin is presented as a fold-increase over the ULN against the peak ALT as a fold-increase over the ULN, on a log₁₀ scale. The measurements displayed of total bilirubin and ALT may, or may not, occur on the same date. Two reference lines, 2xULN for total bilirubin and 3xULN for ALT, are drawn onto the graph in order to divide the plane into 4 quadrants. Normal cases are in the lower left quadrant, potential DILI cases are in the upper right

quadrant (Hy's Law quadrant), while the lower right quadrant is known as the Temple's corollary range (ALT $\geq 3 \times \text{ULN}$ and total bilirubin $< 2 \times \text{ULN}$).

Clinically relevant findings in laboratory data will be reported as baseline conditions (at screening) or as AEs (during the trial) if judged clinically relevant by the investigator, and will be analysed as such.

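### For patients rolling over from the spesolimab arm, the laboratory and vital-sign baseline is an on-drug value, so change and shift tables show change since rollover only

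*SAP*

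**What the plan says.** SAP section 5 gives the general safety rule: "Baseline for safety data, unless otherwise specified, is the last value prior to initiation of treatment in current 1368-0067 study". SAP 7.8.2 repeats it for the laboratory without exception: "For all outputs, the last assessment before the first treatment at Day 1 is chosen as the baseline value". Vital signs (SAP 7.8.3) refer to SAP 6.7, whose default is likewise the last measurement before trial treatment starts.

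For efficacy, SAP section 5 takes the last measurement before any spesolimab: "For prior spesolimab arm in 1368-0052, the baseline in parent trial is used", while prior-placebo patients keep the extension baseline.

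The laboratory outputs in SAP 7.8.2 include differences from baseline, shifts from baseline RCTC grade to the last and worst on-treatment grade, and counts of potentially clinically significant abnormalities. On those counts it adds: "Patients having an abnormal lab value at baseline will be presented separately".

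Protocol 3.1 describes the rollover: "Ideally, the end of treatment (EoT) visit of the preceding trial is the baseline visit (V1) of this extension trial". Protocol 6.2.1 limits the gap to 2 weeks. Protocol 4.1.2 describes the prior-active patients' extension regimen as one "which is half the dose of the 1368-0052 PoCC trial".

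**The concern.** The trial's primary objective is long-term safety, and the prior-spesolimab patients have the longest exposure. Their safety baseline is measured while they are still under the parent-trial dose. A laboratory or vital-sign effect that developed during the parent trial is therefore part of the reference value and drops out of every change computed from it.

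The SAP avoids this for efficacy, in the same section, by going back to the value before the first spesolimab dose. Efficacy and safety changes for the same patient thus have different starting points, and no readable text explains why. No readable section adds a safety table against the pre-spesolimab value.

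The abnormality tables carry a related risk. The group abnormal at baseline mixes patients who were abnormal before any spesolimab with patients who became abnormal on it in the parent trial. A reader cannot separate the two.

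**Working it through.** The plan states no figure to reproduce; Protocol 7.5 reports that no sample size calculation was made.

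**Inputs.** Half-life about 4 weeks (Protocol 1.2.1); residual effect period 16 weeks (1.2.3); gap from parent end of treatment to Visit 1 of 0 to 2 weeks (3.1, 6.2.1); extension dose half the parent dose for prior-active patients (4.1.2).

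**Step 1: is the baseline on drug?** Share of parent end-of-treatment exposure left after a gap of g weeks = 0.5^(g/4), assuming linear kinetics.
- g = 0: 1.00
- g = 2: 0.5^0.5 = 0.71
- g = 16, for comparison: 0.5^4 = 0.06

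A planned gap of 0 to 2 weeks lies well inside the 16-week residual effect period, so the baseline is on drug in every planned case.

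**Step 2: exposure at baseline against later exposure.** Set steady state at the extension dose to 1, with exposure following dose.
- Parent at steady state: 2 × 1.00 = 2.0 with no gap; 2 × 0.71 = 1.4 with a 2-week gap.
- Parent short of steady state (assumed 12 weeks, no loading): 1 − 0.5^(12/4) = 0.875 of steady state, giving 1.75 with no gap and 1.75 × 0.707 = 1.24 with a 2-week gap.

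The range is about 1.2 to 2.0. From 2.0, exposure in week w is 1 + 0.5^(w/4): 1.5 at Week 4 and 1.13 at Week 12, without up-titration.

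**Step 3: what the change tables omit.** For any patient and visit t:

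value(t) − value(Visit 1) = [value(t) − value(parent baseline)] − [value(Visit 1) − value(parent baseline)].

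The last bracket is the change already present at rollover. The planned tables omit exactly that amount. This needs no assumption about dose-response.

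**Step 4: illustration only.** Let D be an effect at parent steady-state exposure (2), with rollover on the same day and later exposure at 1. Use E(c) = c/(EC50 + c); no EC50 is given in the documents.
- Proportional to dose: +0.50 D from the pre-drug value, −0.50 D from Visit 1.
- EC50 = 1: E(1) = 0.500 and E(2) = 0.667, giving +0.75 D and −0.25 D.
- EC50 = 0.1: E(1) = 0.909 and E(2) = 0.952, giving +0.95 D and −0.05 D.
- Saturated: about +1.0 D and about 0.

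Each pair differs by D, as Step 3 requires.

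**Step 5: which outputs depend on this baseline?**
- Dependent: laboratory and vital-sign differences from baseline, the baseline side of the RCTC shift tables, and the split of significant abnormalities by baseline status.
- Not dependent: values by visit; minimum, maximum and last on-treatment values; worst on-treatment grade; AST/ALT counts at 3, 5, 10 and 20 times ULN; AST/ALT combined with bilirubin; and the eDISH plot.
- Not dependent: the TEAE primary endpoint, which is assigned by onset date (SAP 7.8.1).

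**The case against.** A rollover baseline is a legitimate reference for incremental change in an extension. It matches the on-treatment period in SAP 6.1 and the time-at-risk clock in SAP 7.8.1. Protocol 7.2.5, where safety data "will be assessed with regard to possible changes compared to findings before start of treatment", is compatible with it. The two baseline rules stand side by side in SAP section 5, so the difference looks deliberate. All of this stands, and it is why the Visit 1 tables should stay.

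Persisting abnormalities are also not hidden. A persisting grade 2 appears in the shift table as 2 to 2, and patients abnormal at baseline are shown, not dropped. Clinically relevant findings have the adverse-event route: parent-trial events still ongoing are not to be entered as baseline conditions (Protocol 5.2.6.1.1), are re-recorded (5.2.6.2.1) and are included in the AE summaries (SAP 7.8.1). This limits the harm, but it covers only findings judged clinically relevant and does not show which baseline abnormalities arose on drug.

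A reader might infer more: that the safety tables as a whole cannot show what spesolimab did, that a dose-related effect will appear as an improvement, or that the two prior arms will cancel when pooled. The documents do not support these readings. Many outputs do not use baseline, and abnormalities first appearing in the extension are still counted. Reversal needs an effect that weakens at the lower exposure, and none is reported. The healthy-volunteer data point rather to saturation and no laboratory signal: preliminary receptor occupancy of at least 94% at 0.05 mg/kg and above, and no clinically relevant laboratory abnormalities on multiple dosing (Protocol 1.2.1). Cancellation would also need an arm split, which is not given. SAP 6.1 shows tables by prior treatment as well, although the wording suggests an overall display too.

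Finally, the general rule allows exceptions, and some SAP sections (5.4 and 6.5, for example) are not readable. An exception is possible for vital signs; for the laboratory, the statement covering all outputs makes one unlikely.

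**Conclusion.** The point holds for baseline-dependent safety outputs in one arm. For prior-spesolimab patients, laboratory and vital-sign changes and the baseline side of the grade shifts describe change since rollover, and omit whatever was already present. Abnormalities that arose on spesolimab in the parent trial and persist are merged with pre-existing ones.

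That the baseline is on drug follows from the visit timing, half-life and residual effect period. The 71% to 100% of remaining exposure and the ratio of about 1.2 to 2.0 assume linear kinetics; the ratio also assumes exposure proportional to dose and no up-titration. The clinical size cannot be stated: the documents give no laboratory effect and no dose-response. Any sign reversal or cancellation is hypothetical.

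A reader might conclude that the primary analysis is compromised; it is not, because TEAEs are classified by onset date. Nor would a pre-drug baseline prove causation in a single-arm extension. The gap is a missing supplementary reference, worth closing because it is cheap and concerns the longest-exposed patients.

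**What to change.** In SAP section 5, 7.8.2 and 7.8.3:

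1. Keep the Visit 1-based tables, label them *change within the extension*, and read them by prior arm.
2. For prior-spesolimab patients, add change-from-baseline tables (laboratory and vital signs), RCTC shift tables and significant-abnormality tables against the last value before first spesolimab. This is the 1368-0052 baseline, the rule already used for efficacy in this arm.
3. Report the number of prior-spesolimab patients abnormal at rollover who were normal at the parent baseline.

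The cost is SAP wording, one extra table set for part of a trial of about 45 patients, and data work. The efficacy baseline does not itself supply parent laboratory and vital-sign values. These must be linked, and the laboratory values normalised and graded in the same way as the extension data. The prior-spesolimab figures may look slightly less favourable. No trial procedure or new patient assessment is involved.
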